6.7 Safety and tolerability evaluation

The FAS population is used for all safety presentations.

6.7.1 Adverse events

Treatment emergent adverse events (TEAE) are defined as adverse events reported on or after first dose of study treatment. AEs after last dose date, and thus also after study drop-out, are not collected. All AEs reported in the study will be listed.

An AE overview table will be created displaying the number of patients (and percentage) experiencing a treatment-emergent adverse event (TEAE) and the number of TEAEs for: any TEAE, any mild/moderate/severe TEAE, any related/unrelated TEAE, any SAE, any Fatal AEs/Deaths during study and any TEAE leading to study discontinuation. Unique adverse events are determined based on System Organ Class (SOC) and Preferred Term (PT).

All TEAEs are tabulated by SOC and PT within each SOC according to the MedDRA terminology list. TEAEs will also be tabulated by intensity (mild/moderate/severe) and by relationship to study medication (related/unrelated), using frequency counts (number of patients with at least one event, and number of events) and percentage of patients with the event. Similar tables will be created for TEAEs leading to premature discontinuation, SAEs and fatal AEs/deaths, if applicable. In addition, a summary table will be created for TEAEs by intensity and relationship with the IMP including patient identification. All summary tables will be presented by decreasing frequency of occurrence based on SOC and PT.

The summary tables will be accompanied by individual subject listings of *all* reported AEs including information on AE number, actual AE description, date/time of start and end of AE (or ongoing), treatment-emergent (as in: present to first dose), PT (MedDRA), SOC (MedDRA), intensity, relationship, seriousness, action taken and outcome. Pre-existing AEs are not considered to be treatment-emergent, except in case of worsening during/after study treatment (to be collected as separate AE in the database). AEs starting prior to administration of the study drug will only be listed. In this listing, a clear distinction will be made between prior and treatment emergent events.

Separate listings will be created for SAEs and deaths, if applicable.

For summary tables, an AE is considered related if the causality to the study medication is classified as either 'Definitely Related', 'Probably Related' or 'Possibly Related'. Note that missing is imputed as being related according to section 6.2. In other instances, causality will be considered unrelated for summary tables. The original description will be used in listings.

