9. The existence of secondary hyperoxaluria, e.g. hyperoxaluria due to bariatric surgery or chronic gastrointestinal diseases such as cystic fibrosis, chronic inflammatory bowel disease and short-bowel syndrome.
10. Use of antibiotics to which *O. formigenes* is sensitive, including current antibiotic use, or antibiotics use within 14 days of initiating study medication.
11. Current treatment with a separate ascorbic acid preparation. Standard of care vitamin supplement for patients on dialysis are allowed.
12. Pregnancy.
13. Women of childbearing potential who are not using adequate contraceptive precautions. Sexually active females, unless surgically sterile or at least 2 years post-menopausal, must be using a highly effective contraception (including oral, transdermal, injectable, or implanted contraceptives, IUD, abstinence, use of a condom by the sexual partner or sterile sexual partner) for 30 days prior to the first dose of OC5 and must agree to continue using such precautions during the clinical study.
14. Presence of a medical condition that the Investigator considers likely to make the patient susceptible to adverse effect of study treatment or unable to follow study procedures.
15. Participation in any study of an investigational product, biologic, device, or other agent within 30 days prior to the first dose of OC5 or not willing to forego other forms of investigational treatment during this study.

Investigational product, dosage and mode of administration:

The study drug consists of OC5. The dose will be administrated orally with breakfast and dinner as one enteric-coated capsule two times per day. For patients using a gastric tube the capsules may be administered through the tube. The dose will be NLT \geq 1E+09 colony forming units (CFU) per capsule.

Duration of treatment:

Patients will initially be treated for 6 weeks with OC5. Prior to initiation of study medication, the patients will be monitored for 4 weeks. After termination of study medication for the 6-week period the patients will be followed for a 4 weeks follow-up period.

After the end of the 4 weeks follow-up period, the patients will be offered to continue treatment until transplantation. The maximal length of the continued treatment period will be 36 months. A repeated benefit/risk assessment for the patient will be done and documented every three months throughout the continued treatment period.

Criteria for evaluation:

Efficacy:

Primary endpoint:

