6 INVESTIGATIONAL PLAN

6.1 Overall study design and plan

This study is an open label multi-centre study to evaluate the efficacy and safety of OC5 (*O. formigenes*) to reduce plasma oxalate in PH patients on dialysis. It is hypothesised that daily administration of *O. formigenes* facilitates the secretion of endogenously produced oxalate from plasma to the GI tract. The enteric elimination of oxalate in addition to dialysis may help to lower the build-up of extra-renal oxalate in PH patients in ESRD.

Patients will initially be treated for 6 weeks with OC5. The study patients will be monitored for 4 weeks prior to initiation of study medication, as well as 4 weeks of follow-up after termination of study medication. If the patient, in the opinion of the responsible investigator, has a positive effect of the study drug, patients will be offered to continue treatment with study drug after the 4-week follow-up period until transplantation (maximum length of the continued treatment period will be 36 months).

The investigator should confirm that the benefit/risk assessment for the individual patient is considered to be positive and that there are no complications or adverse events that could adversely affect the benefit/risk ratio. A repeated benefit/risk

assessment for the patient will be done and documented every three months throughout the continued treatment period.

Following screening and baseline evaluations eligible patients will receive Oxabact® twice daily for 6 weeks. The dose will be administrated orally with meals as one enteric-coated capsule two times per day preferably with breakfast and dinner. For patients using a gastric tube the capsules may be administered through the tube. The dose will be NLT 1E+09 CFU/capsule.

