11.3 Recording Adverse Events

Each patient will be questioned about AEs at each clinic visit/ following initiation of treatment. The question asked will be "Since your last clinic visit have you had any health problems?" The information can also be obtained from signs and symptoms detected during each examination, observed by the study personnel or spontaneous reports from the study patients or by lab results.

The investigator is to record in the CRFs all directly observed AEs, all AEs as a response of the open question and all AEs spontaneously reported by the patient during the study.

The investigator will record all AEs by:

- Description of event (recorded in standard medical terminology and avoiding abbreviations),
- Start and end date,
- Intensity* (mild, moderate or severe),
- Seriousness (serious or not serious, according to definition),
- Causal relationship, (definitely, possible, probable, unrelated)
- Action taken, (none, treatment required, patient withdrawn, other)
- Outcome of the AE (recovered, recovered with sequelae, death, not recovered)

The Sponsor or delegate will code all AEs and SAEs using MedDRA.

* For each reported AE, the intensity will be recorded. The following definitions of intensity are to be used:

- Mild: A mild AE means awareness of symptoms or signs, but easily tolerated (acceptable).
- Moderate: A moderate AE means enough discomfort to interfere with usual activity (disturbing).
- Severe: A severe AE means incapacity to work or to do usual activity (unacceptable)

If the intensity changes within 24 hours the maximum intensity should be recorded. If the intensity changes over a longer period of time, the changes should be recorded in the CRF.

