6 STATISTICAL ANALYSIS

6.1 General considerations

All evaluations will be explorative in nature, unless stated otherwise. There will be no formal statistical significance testing.

Raw data (in listings) will be presented in the same precision as received. Appropriate rounding will be performed for the summary statistics: arithmetic mean, median, SD (standard deviation) and two-sided 95% confidence limits will be presented with one more decimal than the original data; minimum and maximum values will be presented with the same precision as the original data. In special cases, e.g. after conversion of data, the number of decimals will be determined based on relevance. In frequency tables, percentages will be presented with 1 decimal unless otherwise stated. P-values will be presented with 3 decimals, and those smaller than 0.001 will be replaced by <0.001.

Descriptive statistics presented in summary tables for continuous variables will be the number of non-missing observations (n), arithmetic mean, SD, SE, median, Q1 and Q3, minimum and maximum. All plots will be created using scheduled protocol time or visit on the x-axis. Mean plots will be presenting mean +/- SE. For qualitative data, frequency counts and percentages will be determined. The denominator used when calculating percentages will be the number of subjects in the applicable analysis population.

Baseline is generally defined as the last non-missing and valid measurement/assessment before first dose of study drug. Unscheduled measurements are excluded as baseline value, unless otherwise specified. Change from baseline is calculated as the value at a specific time point minus the value at baseline. For this study, the following definitions are used to define the baseline measurement:

Vital signs: The screening value is used as baseline.

Plasma oxalate: The primary baseline is defined as an average of the available baseline measurements at weeks 2 and 4 (i.e. Visits 2 and 3 respectively). If one baseline measurement is missing for plasma oxalate, the remaining value will be used as baseline value. An additional baseline is the week 10 (Visit 6) assessment of plasma oxalate levels which will serve (only) as a baseline for the assessment of the change in plasma oxalate levels following the 4 week off-treatment period (secondary endpoint). For analyses in the CT phase of the study, a third baseline is defined, being the week 14 value at week 14 of the initial TRT phase.

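### The AE event count has no onset rule, and the AE summaries ignore exposure that is planned to range from 6 to 162 weeks on drug

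*SAP*

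**What the plan says.** **Event counting.** SAP 6.7.1 plans an overview table giving patients, percentages and "the number of TEAEs for: any TEAE, any mild/moderate/severe TEAE, any related/unrelated TEAE", together with SAEs, deaths and discontinuations. That paragraph ends with "Unique adverse events are determined based on System Organ Class (SOC) and Preferred Term (PT". The next paragraph tabulates TEAEs by SOC and PT, "using frequency counts (number of patients with at least one event, and number of events) and percentage of patients with the event", with further tables by intensity and by relationship. The section also promises that "All AEs reported in the study will be listed", with start and end dates among the fields.

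**Recording.** Protocol 11.3 asks for the maximum intensity when intensity changes within 24 hours. Otherwise: "If the intensity changes over a longer period of time, the changes should be recorded in the CRF". One episode may therefore leave several intensity entries.

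**Denominator.** SAP 6.1: "The denominator used when calculating percentages will be the number of subjects in the applicable analysis population". For safety this is the FAS, meaning everyone who took at least one dose.

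**Exposure.** Protocol 6.1: "Patients will initially be treated for 6 weeks with OC5". Some patients then continue, and the Synopsis says: "The maximal length of the continued treatment period will be 36 months". Protocol 11.5.1.2 reports 12 patients treated and 8 entering continued treatment. SAP 6.8.2 derives a treatment duration per patient, but only for the compliance listing. The AE tables in SAP 10.3 (14.3.1.1 to 14.3.1.6) mention neither person-time nor study phase.

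**The concern.** Two features make the AE summaries hard to read.

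First, a uniqueness rule built on SOC and PT alone cannot tell a recurrence from a continuation. If it governs the event count, a patient with several separate infections coded to the same term contributes one event. Infections and gastrointestinal symptoms are among the potential risks in Protocol 4.6.2, and both can recur over three years.

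Second, a patient who took only the 6-week course and a patient treated for three years carry equal weight in every percentage. Safety is a secondary objective, and Protocol 12.1 wants it summarised by frequency among other things. A frequency over such unequal follow-up has no clear time frame.

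**Working it through.** The plan states no AE rate or target, so there is no figure of its own to reproduce.

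**1. What the uniqueness rule can affect**

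- In the overview table the rows are broad categories. Counting a patient once under any TEAE needs no SOC/PT rule, so in that table the rule can act only on the number of TEAEs.
- In the SOC/PT tables, patients are already counted by having at least one event. If events were also reduced to one per patient and term, the patient and event columns would agree in every PT row and the second would be redundant. That points away from collapsing there.
- The rule carries no onset date. It would merge two intensity records of one episode and two episodes a year apart in the same way. The SAP does not say which intensity or causality a merged event would carry, although it tabulates events by both.

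**2. Planned range of time per patient**

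- On drug: 6 weeks for the first course only, and 6 + 156 = 162 weeks for a full continuer. 162/6 = 27-fold. Early withdrawal could give less than 6 weeks.
- AE observation on the protocol schedule: dosing starts after week 4 and AEs are assessed to week 14, so 14 − 4 = 10 weeks. With continued treatment, 10 + 156 = 166 weeks. 166/10 = 16.6-fold. This assumes that continued treatment starts straight after week 14.

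**3. Weight of the non-continuers**

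12 − 8 = 4 patients, or 4/12 = 33% of the denominator. Individual continued-treatment (CT) durations are not given, so the table assumes equal CT time for all 8 continuers and a completed first phase for all 12. Patient-years = person-weeks × 7/365.25.

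| CT weeks each | On drug: 12×6 + 8×CT | Patient-years | Share of the 4 (24 weeks) | Observed: 12×10 + 8×CT | Patient-years | Share of the 4 (40 weeks) |
|---|---|---|---|---|---|---|
| 0 | 72 | 1.4 | 33% | 120 | 2.3 | 33% |
| 52 | 488 | 9.4 | 4.9% | 536 | 10.3 | 7.5% |
| 104 | 904 | 17.3 | 2.7% | 952 | 18.2 | 4.2% |
| 156 | 1320 | 25.3 | 1.8% | 1368 | 26.2 | 2.9% |

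For CT of 52 to 156 weeks, a third of the patients supply between 1.8% and 7.5% of the time, depending on the definition.

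**4. Which denominator fits a rate**

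The protocol schedules AE assessments at weeks 12 and 14, off drug. Dividing by on-drug time would leave those events in the numerator and drop the time. For a first-course-only patient the denominator would be 6 weeks instead of 10, and 10/6 = 1.67, so the rate could be inflated by up to 67%.

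**5. Illustration only: size if events were collapsed**

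Assume a Poisson rate r per patient-year for one term. Expected events are m = r × weeks × 7/365.25. The expected collapsed count is 1 − exp(−m), so the understatement is 1 − (1 − exp(−m))/m.

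| Assumed r | 6 weeks | 58 weeks | 162 weeks |
|---|---|---|---|
| 0.25 | 1% | 13% | 30% |
| 1 | 6% | 40% | 69% |
| 2 | 11% | 60% | 84% |

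Example: r = 1 over 162 weeks gives m = 3.105 and a collapsed count of 0.955, a 69% understatement. The rates are assumptions, because the documents give none.

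**The case against.** **A reader might infer that the SAP discards recurrences and so understates the event burden.** The text does not establish this. The sentence does not say once per patient, and the following paragraph asks for patients and events as separate quantities. The ordinary convention, a patient counted once per term and events counted separately, fits that paragraph. A harmless purpose is also possible: avoiding double counting of one episode recorded at several intensities under Protocol 11.3. This objection stands against any firm claim of collapsing. It does not remove the ambiguity in the overview table, where two programmers could produce different event counts from the same data.

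**A reader might also infer that leaving out exposure makes the figures too low.** That does not follow. A percentage over mixed follow-up would tend to lie below what three years for everyone would show, and above what six weeks for everyone would show. There is no comparator arm, so no between-arm contrast is distorted.

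**Recurrences and timing can be recovered.** With 12 treated patients, the full AE listing gives onset and end dates, Table 14.3.1.5 identifies patients, and dosing dates are listed. The protocol asks only for descriptive safety summaries, and the SAP calls all evaluations explorative. This limits the harm. The summary tables still remain ambiguous and without a time frame.

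**Conclusion.** The point holds as a gap in definition and presentation, not as a demonstrated undercount.

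- **Event rule:** ambiguous. Under the literal reading, the overview table's number of TEAEs may count repeat episodes of one term once. Collapsing in the SOC/PT tables is not established. The percentages in step 5 apply only if collapsing occurs and only at the assumed rates.
- **Exposure:** established from the text. No AE summary uses person-time or a phase split, despite a planned 27-fold range on drug (16.6-fold in scheduled AE observation) and 4 of 12 patients not continuing. Crude percentages are hard to interpret, and the direction of any distortion is not fixed.

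The ranges are planned extremes. Actual continued-treatment durations are not in the documents.

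**What to change.** 1. In SAP 6.7.1, state that the SOC/PT rule applies to patient counts only. Count each AE with a separate onset as one event. Merge only contiguous records of the same episode that differ in intensity, and say which intensity and causality the merged event carries.
2. Beside the number and percentage of patients, add events per patient-year, with the denominator matched to the AE collection window: first dose to last AE assessment, including the off-treatment weeks 11 to 14. Alternatively, give separate summaries for the initial 14-week phase (TRT in SAP 2.2) and for CT, each with its person-time.
3. Reconcile that window with the SAP's own statement (6.1, 6.7.1 and 7) that AEs after the last dose are not collected. For a patient who does not continue, that conflicts with the protocol's assessments at weeks 12 and 14. The start-to-stop duration in SAP 6.8.2 is a starting point, but it ends at the last dose.

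The cost is some SAP wording and one more column. AE onset and end dates and dosing dates are already planned for listing. Rates from 12 patients will be very uncertain, and event counts may rise if the literal reading would otherwise have been programmed.

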6.7.2 Clinical laboratory

The following laboratory safety data are collected for this study:

Hematology	Chemistry	Urinalysis
RBC (Erythrocytes)	Blood Urea Nitrogen	Protein

WBC (Leucocytes)	Electrolytes (Na ⁺ , K ⁺ , Mg ⁺⁺ , Ca ⁺⁺ , HCO ₃ ⁻ , Cl ⁻)	Glucose
Lymphocytes	Glucose	pH
Monocytes	pH/CO ₂	
Neutrophils	Albumin	
Basophils	Alkaline phosphatase	
Eosinophils	ALT	
Platelets	AST	
Haemoglobin	Total bilirubin	
Haematocrit	Total protein	
MCV	Creatinine	
MCHC		

Hematology, biochemistry and urinalysis data will be summarized using descriptive statistics and listed per visit, using protocol visits. Change from baseline will be calculated and presented as well for quantitative data, using the same summary statistics. Screening and week 4 values are omitted from the CFB presentations. If applicable, laboratory safety data collected as additional/unscheduled assessments (i.e. apart from those per protocol) will only be listed and will not be used in summary statistics.

For laboratory safety data, all recorded and determined laboratory safety data will be listed, including information on the reference ranges, if available. In addition, information regarding age at screening and gender will be added to the listing.

Safety laboratory parameters will be presented in the tables and listings in the same units as supplied. In case a parameter is supplied in several different units, it will be investigated if it is possible to convert and present this parameter in standardized units or SI units for the presentation of descriptive statistics. Conversion factors and number of decimals for standardized values used will be supplied or approved by sponsor. If conversion is applicable, then the summaries will be provided in the standardized unit, and listings will contain both the raw data as well as the standardized values.

Lastly, for clinical laboratory parameters, a listing will be created presenting all data that are out of reference range on a per-patient level. The investigator judges the out-of-range values on their clinical significance, and this information will be added as well. In addition, information regarding age at screening and gender will be added to this listing.

6.7.3 Vital Signs

Vital sign data consist of measurements for body weight, pulse rate, systolic and diastolic blood pressure, temperature and respiration rate. Vital signs will be summarized (limited to: n, mean, SD, median, minimum and maximum) and listed per visit, using protocol visits. Change from baseline will be calculated and presented as well, using the same summary statistics. If applicable, vital sign measurements collected as additional/unscheduled assessments (i.e. apart from those per protocol) will only be listed and will not be used in summary statistics.

6.7.4 Prior and concomitant medication

The use of prior and concomitant medication will be listed for all patients: included will be the medication generic name, WHO coding information, dose, route of administration, start and stop date, frequency and reason for administration, as well as information if given for an AE. A differentiation (flag) will be made between prior and concomitant medication.

In addition, summaries for prior and concomitant medications will be created, presenting the number of patients with any prior/concomitant medication, and the number of patients for each ATC System Main Therapeutic Group (2nd level of WHO classification), irrespective of duration of receipt, frequency or dose.

If a comedication is started prior to first dose of study treatment, this is considered prior medication. Concomitant medication is defined as started before first study treatment and continuing thereafter or starting on/after first dose date of study medication. As a consequence, several medications may be defined both as prior as well as concomitant. Whether a medication is considered prior/concomitant/both in case of partially missing dates is determined using the rules for missing data detailed in Section 6.2.

